7.1.2 Time to unfavourable efficacy outcome

Time to unfavourable efficacy outcome is defined as the time from randomisation to the first event that results in the definition of an unfavourable efficacy outcome for that patient (as defined in Section 3.2). Patients that do not culture convert during the treatment and follow-up phases (i.e. fail to have 2 consecutive culture negative results), and have not otherwise been called unfavourable, will be called unfavourable at the date of the last visit when a culture positive result was obtained. Patients classified as favourable or not assessable will be censored in this analysis at the date of collection of sputum that yielded their last negative culture result.

Median time to unfavourable efficacy outcome will be calculated for Regimen B, Regimen C, and Regimen D using the Kaplan-Meier estimator.

A hazard ratio with corresponding two-sided 95% confidence intervals and p-value will be estimated for the comparison of Regimen B with Regimen C, and Regimen B with Regimen D. A Cox Proportional Hazards model will be used, adjusted for randomisation protocol (as defined in Section 1.6) and the stratification factor HIV status with the three categories of: HIV negative; HIV positive with CD4 count ≥350 cells/mm³; and HIV positive with CD4 count <350 cells/mm³.

The equality of survivor functions for time to unfavourable efficacy outcome for Regimen B and Regimen C, and Regimen B and Regimen D, will each be tested using a Log rank test, stratified by randomisation protocol (as defined in Section 1.6) and the randomisation stratification factor HIV status with the three categories of: HIV negative; HIV positive with CD4 count ≥350 cells/mm³; and HIV positive with CD4 count <350 cells/mm³.

The assumption of proportional hazards between the two comparisons will be tested using the proportional hazards test based on the Schoenfeld residuals after fitting the Cox Proportional Hazards models. In the case where there is adequate evidence that the proportional hazard assumptions are violated at the 5% level (i.e. p<0.05), methods where proportional hazards is not a necessary assumption will be used, such as the Wilcoxon test of equality of survivor functions and restricted mean survival time.

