4.4 Per protocol (PP)

The PP population will be the same as the mITT population with the exclusion of patients not completing a protocol-adherent course of treatment, other than for treatment failure, change of treatment for an adverse event or death. Treatment failure is defined as failure to attain and maintain culture negativity until the end of allocated treatment.

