5.3 Visit window definitions

In Stage 2, patients will be assessed at screening, randomisation (Week 0), Week 1, Week 2, Week 3, Week 4, after which they will be seen 4-weekly until Week 52, after which they will

be seen 8-weekly until Week 84, after which they will be seen 12-weekly until Week 132 post randomisation.

Baseline is defined as the date of randomisation (Study day 1). For all variables the baseline measurement will be the one taken at the randomisation visit. If this does not exist the measurement from the screening visit will be used if available. For ECG measurements, the mean of all available measurements from the randomisation visit will be used.

For the purpose of analysis, each scheduled visit will have a window before and after the target date, calculated from date of randomisation. When referring to a visit hereon, this implies within the defined visit window as specified below in Table 2.

Table 1: Visit window definitions

Visit	Target study day	Analysis window (study days)
Screening /	1	Date of screening consent – 1
Baseline		
Week 4	29	2-42
Week 8	57	43-70
Week 12	85	71-98
Week 16	113	99-126
Week 20	141	127 – 154
Week 24	169	155 – 182
Week 28	197	183 – 210
Week 32	225	211 – 238
Week 36	253	239 – 266
Week 40	281	267 – 294
Week 44	309	295 – 322
Week 48	337	323 – 350
Week 52	365	351 – 392
Week 60	421	393 – 448
Week 68	477	449 – 490
Week 76	533	491 - 574*
Week 84	589	575 – 630
Week 96	673	631 – 714 [†]
Week 108	757	715 – 798†
Week 120	841	799 – 882†
Week 132	925	883 – no upper bound [†]

NB. Study day 1 =date of randomisation

Any visit, scheduled or unscheduled, that falls into the analysis window will be assigned to that visit for the purpose of analysis. If two visits fall within the same interval, the one closest to the target date will be used for analyses by visit, so that there is only one unique visit for each patient and analysis time-point.

^{*} see section 3.1.1

[†] see section 5.3.1

There are additional study visits at Weeks 1, 2 and 3 only for ECG monitoring. For the analysis of ECG data only, there will be additional visit windows: Week 1 (2-11), Week 2 (12-18), Week 3 (19-25) and the Week 4 visit window will be modified to (26-42).

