7 ANALYSIS OF SECONDARY OUTCOMES

7.1 Efficacy outcomes

Secondary efficacy analyses will be carried out on i) data censored at Week 76, and ii) data from all visits occurring on or before the projected Week 96 visit of the last patient randomised i.e. approximately end of November 2021 (long-term efficacy data). A participant's scheduled last efficacy visit will be their latest scheduled trial visit on or before this date. In addition to the comparisons detailed below, analyses of the long-term efficacy data will include comparisons of Regimen C with Regimen D. Comparisons of Regimen C and Regimen D using data up to Week 76 were carried out at the time of the primary analysis but considered exploratory.

Secondary efficacy outcomes will be analysed on the mITT analysis population with the exception of the analysis of favourable outcome at Week 132 to determine the non-inferiority of Regimen C to Regimen B which will be analysed on the mITT, PP and mPP populations.

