7.1.3 Time to failure or recurrence

Favourable outcome for each participant will be re-classified according to the likelihood that it was a *Failure or Recurrence (FoR) event* on a five-point Likert scale: Definite, Probable, Possible, Unlikely, and Highly Unlikely⁷.

An event will be considered *Highly Unlikely* to be a FoR event only if there is evidence of durable cure; i.e. the primary outcome classification of favourable which required completion of follow-up with negative cultures. A *Definite* FoR event requires clear bacteriological evidence of failure or recurrence (excluding a proven reinfection with exogenous strain of *M. tuberculosis*), a *Probable* FoR event requires some evidence for failure or recurrence (clinical, bacteriological, or radiological) in the absence of clear bacteriology. The remaining participants will be classified as possible or unlikely based on their data. Time of the FoR event/censoring is the same as defined in the time to unfavourable outcome analysis (see Section 7.1.2). The FoR classification will reviewed by an independent clinician, blinded to treatment.

In the time to FoR analyses, the main groups of interest are those classified as having a Definite or Probable FoR event, with censoring of Possible, Unlikely and Highly Unlikely events at the time of the censoring event which met criteria for Unfavourable or Not Assessable in the primary analysis.

Median time to FoR will be calculated for Regimen B, Regimen C, and Regimen D using the Kaplan-Meier estimator.

A hazard ratio with corresponding two-sided 95% confidence intervals and p-value will be estimated for the comparison of Regimen B with Regimen C, and Regimen B with Regimen D. A Cox Proportional Hazards model will be used, adjusted for randomisation protocol (as defined in Section 1.6) and the stratification factor HIV status with the three categories of: HIV negative; HIV positive with CD4 count ≥350 cells/mm³; and HIV positive with CD4 count <350 cells/mm³.

The equality of survivor functions for time to failure or recurrence for Regimen B and Regimen C, and Regimen B and Regimen D, will each be tested using a Log rank test, stratified by randomisation protocol (as defined in Section 1.6) and the randomisation stratification factor HIV status with the three categories of: HIV negative; HIV positive with CD4 count ≥350 cells/mm³; and HIV positive with CD4 count <350 cells/mm³.

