The secondary non-inferiority outcome at Week 132 for Regimen B compared to Regimen C will be analysed using time to unfavourable outcome, thereby using information on all participants. Data from participants whose scheduled last efficacy visit is before Week 132 will be censored at the time of their last visit, unless they have already become unfavourable. Non-assessable participants will be included in the time to event analysis and censored at the time of their last visit.

The survival curve for each combination of strata (randomised protocol and HIV status) will be calculated using a Cox model adjusting for stratification factors and randomised group. The average survival curve for each randomised group will be estimated as a weighted average of the corresponding stratum-specific survival curves, with weights proportional to the number of individuals in each stratum in the randomised group at baseline. The mean of these differences at week 132 is the point estimate for the difference in overall survival function between Regimen C and Regimen B. A two sided bias-corrected 95% CI for the difference in proportion (Regimen C – Regimen B) will be calculated with bootstrap standard errors. Bootstrap standard errors for the risk difference will be used so that the CI of the risk difference (estimated by the risk difference ± 1.96 se assuming the bootstrap distribution is approximately Normal) is bounded between -1 and 1. The bootstrapping will sample 1000 times and be stratified by stratification factors. The seed for the bootstrap simulations will be stored to enable replication of results.

Non-inferiority will be shown if the upper bound of the 95% confidence interval of the difference in proportion of favourable outcomes at Week 132 between Regimens B and C is less than the 10% margin of non-inferiority; this must be shown in both the mITT and PP populations. If non-inferiority is demonstrated, then superiority of Regimen C compared to Regimen B will be declared if the upper bound of the 95% confidence interval of the difference in proportion of favourable outcomes at Week 132 between Regimens B and C is less than zero. For this analysis, the mITT population will be primary and the PP and mPP populations will be sensitivity analyses.

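### SAP 7.1.2 dates never-converters at their last positive culture without limiting this to post-randomisation samples, so some early losses get an event time of zero or below

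*SAP*

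**What the plan says.** SAP 7.1.2 sets the clock: "Time to unfavourable efficacy outcome is defined as the time from randomisation to the first event" that makes the patient unfavourable under SAP 3.2. It then adds a special rule for patients who never have two consecutive negative cultures "and have not otherwise been called unfavourable": such a patient "will be called unfavourable at the date of the last visit when a culture positive result was obtained". The sentence sets no earliest date, does not exclude baseline cultures, and does not say what happens if the resulting time is zero or negative.

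The date is used again twice. In SAP 7.1.3, "Time of the FoR event/censoring is the same as defined in the time to unfavourable outcome analysis". In SAP 7.1.4, the Week 132 non-inferiority comparison of Regimens B and C "will be analysed using time to unfavourable outcome, thereby using information on all participants".

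On population, SAP 7.1 states that "Secondary efficacy outcomes will be analysed on the mITT analysis population", with the PP and mPP populations added for the Week 132 non-inferiority comparison.

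**The concern.** The definition asks for the first qualifying event, but the rule for never-converters takes the last positive culture. This goes wrong at both ends of follow-up.

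At the early end, the last positive culture of a patient who is soon lost may be the sample that qualified them for the trial. The event then falls on or before the day the clock starts, even if the patient was followed for some weeks. Some survival routines exclude records with a non-positive time and others keep them at the origin; the SAP does not say which applies. If they are excluded, patients who count as unfavourable in the primary analysis disappear from an analysis described as using every participant.

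At the late end, a patient who stays positive and meets no other criterion has the event pushed back by each new positive culture. Among such patients, longer positivity reads as longer time free of failure.

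**Working it through.** The plan gives no figure to reproduce, so the check applies the rule as written and then sizes it on assumed counts.

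**Inputs**
- Every mITT patient has a positive culture at screening or randomisation (SAP 4.3). A last positive date therefore always exists and may be a baseline date.
- Randomisation follows screening consent by at most 4 weeks (Protocol 5.4.2).
- No sputum is collected at Weeks 1 to 3, so the first post-baseline sample is at Week 4 (Protocol 8.1.1, Stage 2).
- Unfavourable item 9 is a positive among the last two cultures; item 10 is no culture in the Week 76 window (SAP 3.2). Neither is given an event date.

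**Does the rule reach early losses?** If a patient's last two cultures were both negative, they would be two consecutive negatives and the patient would have converted. So every never-converter also meets item 9. Listing all 373 never-converting sequences of 1 to 10 cultures with a positive in the first two positions confirmed this without exception. The exemption for patients otherwise called unfavourable therefore cannot include item 9, or the rule would apply to nobody. It has to mean that no separately dated event, such as a treatment change or death, came first. On that reading early losses are covered.

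**Event times under the rule**

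| Culture history, no other unfavourable event | Event time (weeks) |
|---|---|
| Randomisation positive, lost before Week 4 | 0 |
| Only the screening sample positive, lost before Week 4 | below 0, to about -4 |
| Randomisation positive, Week 4 negative, then lost | 0, although observed to Week 4 |
| Randomisation and Week 4 positive, then lost | 4 |
| Positive at every visit to Week 76 | 76 |

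**Size at the early end.** Assume 200 per arm with 20% (B) and 18% (C) unfavourable, matching the planned 80% and 82% favourable, and use simple proportions in place of the survival estimate. If m events are dropped from Regimen C only, its unfavourable proportion is (36 - m)/(200 - m):
- m = 2: 34/198 = 17.2%
- m = 4: 32/196 = 16.3%
- m = 8: 28/192 = 14.6%

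Against 18.0%, these are shifts of 0.8, 1.7 and 3.4 points, to be read against a 10-point margin. If both arms lose the same m, the difference C - B is -2.02, -2.04 and -2.08 points instead of -2.00.

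**Size at the late end.** Dating m patients at Week 76 instead of at the scheduled end of treatment (Week 40) lengthens that arm's restricted mean to Week 76 by m x (76 - 40)/200 weeks. That is 0.36, 0.72 or 1.44 weeks for m = 2, 4 or 8. A simulation with the same arm sizes and event counts (other events uniform from Week 4 to Week 76) compared dating persistent failures at Week 24 with dating them at Week 76. The hazard ratio C/B was:
- 4 in each arm: 0.890 against 0.889
- 8 in C, 2 in B: 0.897 against 0.874
- 2 in C, 8 in B: 0.883 against 0.905

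**The case against.** **Most persistent failures will be dated earlier.** The rule applies only when nothing else has made the patient unfavourable. Regimen change, retreatment, disallowed extension, certain new drugs and death are separate items in SAP 3.2. Protocol 9.1 lists persistent positive bacteriology as a reason to modify treatment, and SAP Figure 2 classes a patient retreated after a positive smear at the Week 24 check as unfavourable. This stands. A reader might infer that persistent failures in general become the latest events; the documents support that only for the residual group with no such event.

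**Delay beyond Week 76.** A reader might infer that in the long-term data the event can be 132 - 40 = 92 weeks after the scheduled end of treatment. The literal sentence allows a date after Week 76. But every never-converter is already unfavourable at Week 76, SAP 7.1.4 carries that status forward, and SAP 7.1.2 asks for the first event. The 92-week figure is not supported; what is missing is an explicit cap.

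**Zero or below depends on the reading.** SAP 7.1.2 speaks of not converting during the treatment and follow-up phases, and SAP 5.2 starts treatment at randomisation, so screening samples might be meant to be out of scope. SAP 5.3 also numbers the randomisation day as study day 1; if times were coded that way, only screening-only positives would be non-positive. Both readings are possible, but neither is stated for this date. Excluding screening samples leaves a screening-only positive with no date. Coding as day 1 still places the event before any follow-up for a patient seen at Week 4.

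**Item 10 may already cover early losses.** If so, they fall outside the rule, but item 10 has no date, so the gap moves rather than closes.

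**Existing safeguards.** SAP 7.1.4 includes a proportion-based sensitivity analysis that does not use these dates, restricted to participants randomised early enough to reach Week 132. In SAP 7.1.3, early losses without definite or probable evidence are censored and not counted as events, although at the same date. These limit the damage but do not repair the main Week 132 analysis.

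**Conclusion.** The rule is wrong as written for early losses. Applied literally, it gives an event time of 0 when the last positive is the randomisation sample, and below 0 when only the screening sample was positive. No handling is specified. The same dates feed SAP 7.1.3 and the Week 132 non-inferiority analysis. For the residual never-converters with no treatment change, retreatment or death, it also makes the event later with each positive culture, up to Week 76.

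The likely effect is small. The documents give neither the number of patients nor the software's behaviour, so the shifts of 0.8 to 3.4 points rest on assumed counts dropped from one arm only. Balanced losses nearly cancel, and the simulated hazard ratio moves by about 0.02 only under an 8 to 2 imbalance. The primary Week 76 analysis is a stratified difference in proportions and does not use these dates.

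A reader might also infer that SAP 4.4 requires failure to be dated at the end of treatment, since "Treatment failure is defined as failure to attain and maintain culture negativity until the end of allocated treatment". That sentence decides who is excluded from the PP population; it does not set an event date. SAP 5.5 lets culture-negative status be reached during follow-up, before any retreatment. End-of-treatment dating is a defensible alternative that the plan does not impose.

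**What to change.** In SAP 7.1.2, carried into 7.1.3 and 7.1.4, for never-converters with no earlier unfavourable event:
- use only cultures taken after randomisation to set the date;
- if there is no post-randomisation positive, use the last attended visit, with a minimum of one day after randomisation so that no event is dropped;
- in the long-term data, date no never-converter later than the Week 76 visit.

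Add a sensitivity analysis that dates these patients at the scheduled end of allocated treatment, including any permitted extension. Tabulate by arm how many patients the rule affects.

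The cost is a few lines of SAP text and a small change to the date derivation; no new data are needed. SAP 6.1.3 and 7.1 indicate that Week 76 comparisons have already been run. Any Week 76 time-to-event results already produced should be re-reported under the revised dating as a labelled sensitivity analysis.

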Stage 2 of the STREAM trial will involve the investigation of two alternative regimens, both variations on Regimen B, incorporating the drug bedaquiline. The first of these investigational regimens, Regimen C, involves the removal of the injectable, kanamycin, in order to avoid the associated risks of ototoxicity and renal toxicity. The second investigational regimen, Regimen D, investigates the possibility of treatment being further shortened to 28 weeks, with a shorter duration of kanamycin and isoniazid and also whether ethambutol, which is of questionable efficacy, and prothionamide, commonly associated with severe gastric symptoms, can be removed.

The primary objective of Stage 2 is to assess whether Regimen C is non-inferior to Regimen B.

As the final results of STREAM Stage 1 would not be available until late in enrolment for Stage 2, and due to the urgent public health and clinical need to improve treatment of MDR-TB, Stage 2 was started without randomised controlled trial evidence that Regimen B is non-inferior to Regimen A. Regimen B was selected as the control arm for Stage 2 after careful consideration.

The final analysis of STREAM Stage 1 made public at The Union Conference in October 2018 found that 78.8% of participants on Regimen B had a favourable outcome at 132 weeks from randomisation compared to 79.8% on Regimen A. After adjustment for the randomisation stratification factors of HIV status and centre, the difference in efficacy between the regimens was 1.0%, 95% CI (-7.5 to 9.5%). The upper bound of the confidence interval met the pre-specified 10% non-inferiority margin. The proportions of patients who experienced a Grade 3 or greater adverse event at any time during treatment and follow-up, the primary safety outcome, was also similar on the two regimens (48.2% on the shorter regimen compared to 45.4% on the longer regimen).

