2 SAMPLE SIZE

2.1 Power to demonstrate non-inferiority in the primary efficacy outcome (primary objective relating to Regimens B and C)

Stage 2 aimed to randomise at least 200 patients to each of Regimen B (B_{mox} or B_{lev}) and Regimen C. This revised sample size in protocol version 8.0 was determined based on the assumption that the proportion of patients with a favourable efficacy outcome at Week 76 is 80% for Regimen B (estimated based on preliminary Stage 1 results) and 82% for Regimen C (based on an anticipated minimum benefit in efficacy of using 40 weeks treatment with bedaquiline compared to 16 weeks treatment with kanamycin). Using a non-inferiority margin of 10% and a one-sided significance level of 2.5%, 172 evaluable patients will be required in each of the two regimens to demonstrate non-inferiority of Regimen C to Regimen B with 80% power. To account for 14% of patients excluded from the primary per protocol efficacy analysis population, a total of 400 patients will need to be enrolled across the 2 regimens.

A sample size of 400 patients enrolled to the comparison of Regimens B and C is necessary to rule out an 8% increased mortality in Regimen C compared to the 8% observed on Regimen B in the preliminary analysis of STREAM Stage 1. This will provide 80% power with a one-sided 0.025 type I error.

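### At the planned success rates the Kaplan-Meier median in SAP 7.1.2 and 7.1.3 is not expected to be reached in Regimens B and C, which leaves failure or recurrence with no absolute estimate by arm

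*SAP*

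**What the plan says.** SAP 7.1.2 (time to unfavourable efficacy outcome): "Median time to unfavourable efficacy outcome will be calculated for Regimen B, Regimen C, and Regimen D using the Kaplan-Meier estimator".

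SAP 7.1.3 (time to failure or recurrence): "Median time to FoR will be calculated for Regimen B, Regimen C, and Regimen D using the Kaplan-Meier estimator".

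Both sections add a Cox hazard ratio and a stratified log-rank test for B against C and B against D. Restricted mean survival time appears only as an example of what to use if the proportional-hazards test gives p<0.05. Neither section asks for a Kaplan-Meier proportion at a fixed time or for a lower quantile. Section 7.1.3 counts only Definite and Probable FoR as events and censors the other categories. It also repeats the analysis in the subgroups of 6.3.

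On expected rates, SAP 2.1 assumes that "the proportion of patients with a favourable efficacy outcome at Week 76 is 80% for Regimen B", and 82% for Regimen C. Protocol 2.2 reports from Stage 1 that "78.8% of participants on Regimen B had a favourable outcome at 132 weeks from randomisation". Protocol 11.4.3 expects about 100 patients on Regimen D. No expected success rate for D is given.

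**The concern.** A median time to event can be estimated only when at least half of the Kaplan-Meier probability has been used up. The wording suits SAP 7.1.1, where most patients are expected to convert their smear and culture. In 7.1.2 and 7.1.3 the event is a bad outcome that the trial expects in about one patient in five, or fewer for FoR. At those rates the stated summary would read 'not reached' in the main comparison arms, and again in most FoR subgroup tables.

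What is at stake is the reporting of FoR on the absolute scale. The trial's objective and its 10% margin are differences in proportions, and Protocol 2.2.1 names failure or relapse as a risk for Regimens C and D. A hazard ratio beside an empty median tells a reader little about how many patients failed or relapsed in each arm.

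**Working it through.** **1. The plan's own figure.** SAP 2.1: "Using a non-inferiority margin of 10% and a one-sided significance level of 2.5%, 172 evaluable patients will be required in each of the two regimens". The stated power is 80%. A standard normal-approximation formula gives n per arm = (1.960 + 0.842)² × (0.80×0.20 + 0.82×0.18) / (0.10 + 0.02)² = 7.849 × 0.3076 / 0.0144 ≈ 168. That is within 3% of 172. With the plan's figures, 2 × 172 = 344 and 344 / 0.86 = 400. The 80% and 82% rates are therefore the ones on which the trial was sized.

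**2. Where the curves should end.** The median needs S(t) ≤ 0.5.
- B at Week 76: S ≈ 0.80, about 34 of 172 unfavourable. Half would be 86.
- C at Week 76: S ≈ 0.82, about 31 of 172.
- B at Week 132, at the Stage 1 rate: S ≈ 0.79.

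**3. Where a median would lie under a constant hazard.** Median = t × ln 2 / (−ln S(t)).
- B: 76 × 0.693 / 0.223 ≈ 236 weeks.
- C: 76 × 0.693 / 0.198 ≈ 265 weeks.
- B at the Stage 1 Week 132 rate: 132 × 0.693 / 0.238 ≈ 384 weeks.

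Efficacy follow-up ends by Week 132.

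**4. Simulation with the SAP's censoring rule.** There were 300 runs per scenario, and 20% of unfavourable outcomes were assumed to be missing Week 76 cultures. At 18% to 21.2% unfavourable, the median was reached in 0% of runs, at both the Week 76 and the long-term cut. S at the end of follow-up was about 0.75 to 0.82. This holds when missing-culture outcomes are dated at last contact or at Week 76.

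The SAP gives no date for those outcomes. If they are dated at the end of the window (day 574), after favourable patients have been censored, the Week 76 curve drops on its last day. A median of day 574 then appeared in 96% to 100% of runs. It is an artefact, and it did not occur with the long-term data.

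**5. FoR.** Section 7.1.3 uses the same event and censoring times as 7.1.2 but counts only some of the events. At each time the risk set is the same and the number of events is no larger. The FoR curve therefore lies on or above the curve for unfavourable outcome, and its median is harder to reach.

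**6. Regimen D (n = 100; all rates are assumptions).** The chance that at least half are unfavourable is 2×10⁻¹¹ at 20%, 2×10⁻⁵ at 30%, 0.027 at 40%, 0.18 at 45% and 0.54 at 50%. In simulation at 40%, the median was reached in 2% to 24% of runs, with missing cultures dated at last contact or Week 76.

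**7. What a fixed-time summary would give at the planned rates.** 95% CI = p ± 1.96 × √(p(1−p)/172).
- B: 20%, 14% to 26%.
- C: 18%, about 12% to 24%.

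**The case against.** The strongest reply is that little is lost. 'Not reached' is a legitimate result, and the hazard ratio, the log-rank test and the primary analysis do not use the median. That stands.

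It is also fair that much absolute reporting exists already:
- SAP 6.1 gives the stratified Week 76 risk difference for B–C and repeats it for B–D.
- SAP 7.1.4 estimates average survival curves by arm and their difference at Week 132 with a bootstrap interval, and repeats this for other pairs, including D and B.
- SAP 6.2 tabulates by arm the event that made each patient unfavourable and whether it was bacteriologically related.
- SAP 8.2 tabulates WHO outcomes by arm, with a category for relapse after treatment success.

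A reader might infer that neither endpoint has any absolute estimate in the SAP. For unfavourable outcome the first two items rule that out. For FoR the gap remains: the tables in 6.2 and 8.2 do not use the five-point FoR classification and make no allowance for censoring. An Extensive Stage 2 SAP is mentioned but was not available, so the gap is shown only for this SAP.

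A fixed-time FoR proportion also has a weakness. One minus Kaplan-Meier treats Possible and Unlikely outcomes, which can include deaths and treatment changes, as independently censored. Section 7.1.3 already tests that assumption with censoring weights and multiple imputation. The caveat belongs beside the estimate but does not rule it out.

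**Conclusion.** The point holds for Regimens B and C. At 80% and 82% favourable at Week 76, and 78.8% on B at Week 132, the only unconditional summary by arm in 7.1.2 and 7.1.3 is not expected to be reached. The practical loss is the missing absolute FoR estimate by arm. This is a cheap improvement and no planned inference is affected.

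Three stronger readings are not supported:
- **That the median cannot be reached in any arm.** The conclusion rests on planning rates. No rate is documented for D, where the median would be reached only if close to half of patients were unfavourable.
- **That a binomial tail gives the probability of reaching a median.** For B (n = 172, 20%) the chance of 86 or more unfavourable is 1.7×10⁻¹⁸. That shows how far the planned rate is from one half. A Kaplan-Meier median also depends on event dates and on who is still at risk, as the day-574 artefact shows.
- **That the sentence was copied from the conversion endpoint in 7.1.1.** The wording is similar, but the documents do not say how it arose.

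**What to change.** **In 7.1.3**, replace the median with the cumulative FoR proportion by arm at Week 76, and at Week 132 from the long-term data. Give B–C and B–D differences with 95% confidence intervals. State that one minus Kaplan-Meier treats Possible and Unlikely events, including deaths and treatment changes, as independently censored. Alternatively, use a cumulative incidence estimate with those as competing events.

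**In 7.1.2**, replace the median with Kaplan-Meier proportions by arm at the same two times, and cross-refer to 6.1 and 7.1.4 for the differences.

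**In both**, state the date assigned to an outcome that is unfavourable for lack of a Week 76 culture. The date also moves the fixed-time estimate: in the simulation at 20% unfavourable (n = 200), S at the Week 76 cut was about 0.80 with last-contact dating and 0.76 with Week 76 dating.

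**Keep medians in 7.1.1** for smear and culture conversion.

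The cost is SAP wording and slightly more output. The Kaplan-Meier proportions come from the fit already planned, and no new data are needed. The FoR proportion carries the censoring assumption that 7.1.3 already examines.
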